## **5. Results analysis**

The data contained in the CRFs will be entered into a database for data analysis and preparation of the final report.

The socio-demographic and clinical characteristics and other variables of interest of the patients included in the study will be described. Data will be presented as mean  $\pm$  SD; categorical data will be shown as percentage of positive patients.

The relationship between two qualitative variables will be calculated using the chi-squared test or Fisher's exact test (frequency  $< 5$ )

For ordinal variables, linear regression will be calculated using Kendall's tau coefficient.

Quantitative variables will be compared using the Student's t-test (< 2 categories), analysis of variance [ANOVA] (> 2 categories), linear regression test and Scheffé's multiple comparisons test or U Mann Whitney.

The linear relationship between the quantitative variables will be calculated using Pearson's correlation coefficient or Spearman's rank correlation test (when variable not normally distributed).

Changes *versus* baseline will be analyzed by Wilcoxon non-parametric test or Mc Nemar test.

A logistic regression model will be set in order to determine whether the initial extent of the inflammation, mBI, is related to disease resolution

Level of significance will be set at 0.05. The SPSS version 19.00 software (SPSS Inc., Chicago, IL, USA) will be used for all analyses.

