## 2. Objectives

### **-Primary objective:**

Evaluate the resolution of the disease, by means of reduction of modified bleeding index (mBI), by individualized OHI and proper oral hygiene measures conducted by the patient after 1 and 3 months of protocol instauration in comparison to the combination of individualized OHI and professional mechanical debridement.

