### **-Secondary objectives:**

- Evaluate microbiological changes by individualized OHI and proper oral hygiene measures conducted by the patient after 1 and 3 months of protocol instauration in comparison to the combination of individualized OHI and professional mechanical debridement.
- Determine if the extent of inflammation measured as the initial mBI could have any impact in the PM resolution after treatment.

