## 3. Hypothesis

- The proper oral hygiene measures conducted by the patient after individualized OHI will achieve resolution of PM in a clinically relevant proportion of patients.
- The proper oral hygiene measures conducted by the patient after individualized OHI will reduce the expression of peri-implant pathogens as much as the combination of individualized OHI and professional mechanical debridement in a clinically relevant proportion of patients.
- The proper oral hygiene measures conducted by the patient after individualized OHI will reduce mBI as much as the combination of individualized OHI and professional mechanical debridement in a clinically relevant proportion of patients.
- The extent of inflammation measured as the mBI could be related with the degree of resolution of the disease according to the treatment.

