### **Clinical, radiographic and microbiological examination**

At baseline, 1 (1m) and 3 months (3m) after treatment, two calibrated examiners ([name] and [name]) will record the following clinical variables using an electronic, pressure-calibrated probe (PA\_ON Probe, Orange Dental®, [name], Biberach, Germany), with a standardized probing force of 0.20 N.

At the full-mouth level, the following parameters will be evaluated:

- (1) Full mouth plaque Index (FMPI), assessed dichotomously at four sites per tooth (mesial, buccal, distal, and lingual).
- (2) Full mouth bleeding index (FMBI), assessed dichotomously as presence or absence of bleeding after 30 seconds of gently probing (Ainamo and Bay, 1975).
- (3) Full mouth probing pocket depth (FMPPD), measured at six sites around each tooth, except third molars.

At local level, in six sites around each implant, the following clinical variables will be recorded:

- (1) Modified plaque index (mPI) (Mombelli et al., 1987)
- (2) Modified bleeding index (mBI) (Mombelli et al., 1987), dichotomized in presence/absence of bleeding and selected as the primary outcome (BOP).
- (3) Suppuration on probing (SOP), assessed dichotomously as presence or absence of suppuration within 30 seconds after probing.
- (4) Implant probing pocket depth (PPDi), measured from the mucosal margin to the bottom of the probable pocket.
- (5) Implant mucosal recession (MRI), measured from the implant neck to the mucosal margin.

Disease resolution will be considered when a mBI <0.16 is achieved, as it was established in the last consensus performed to develop the clinical practice guidelines on the treatment of peri-implant diseases (Herrera et al. 2023).

Individual acrylic resin occlusal stents, exhibiting six vertical grooves per implant (mesiobuccal, midbuccal, distobuccal, mesiolingual, midlingual and distolingual), will be built in order to allow a reproducible direction and angulation during probing.

A periapical radiograph of all implants involved in the study will be taken using a paralleling cone technique and a film-holder (7mA- 60kV/20ms) at baseline and at 3 months after treatment, in order to detect any loss of supporting bone.

Furthermore, sampling for microbiological test will be conducted at baseline, 1m and 3months after treatment.

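### The group comparisons name no covariate although baseline mBI is recorded in every patient; adjusting would sharpen the comparison of quantitative mBI and help little for resolution

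*Combined protocol and SAP*

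**What the plan says.** The primary objective compares OHI alone with OHI plus debridement at 1 and 3 months, "by means of reduction of modified bleeding index (mBI"). mBI is among the variables recorded "At baseline, 1 (1m) and 3 months (3m) after treatment", and Annex 1 lists it at all three visits. The sample-size section makes the patient the unit of analysis, averages over eligible implants, and plans 28 patients per group with 15% dropout. Randomisation uses permuted blocks of four; no stratification by mBI is mentioned.

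For comparisons, Section 5 states: "The relationship between two qualitative variables will be calculated using the chi-squared test" (or Fisher's), and "Quantitative variables will be compared using the Student's t-test", followed by ANOVA, a linear regression test, Scheffé comparisons and Mann-Whitney. No covariate is named for any of these. Baseline values otherwise enter through paired Wilcoxon and McNemar tests of change, and through one model: "A logistic regression model will be set in order to determine whether the initial extent of the inflammation, mBI, is related to disease resolution".

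That model corresponds to the secondary objective, which asks whether initial mBI "could have any impact in the PM resolution after treatment". The fourth hypothesis in Section 3 is worded differently: mBI "could be related with the degree of resolution of the disease according to the treatment".

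**The concern.** The plan identifies a likely prognostic variable, collects it at no extra cost, and then names no use for it in the group comparison. With 28 patients per group, precision is scarce. When a baseline measurement correlates with its follow-up value, conditioning on it narrows the interval for the group difference. Randomisation without stratification by mBI also leaves chance imbalance to the analysis.

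A secondary matter is a mismatch of wording. The logistic model names baseline mBI but not treatment group. If the fourth hypothesis means that mBI matters differently under the two treatments, no analysis stated in Section 5 examines that.

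**Working it through.** **Inputs from the protocol.** 28 per group; 15% dropout, so 28 × 0.85 = 23.8, about 24 per group; resolution 66.6% (control) and 50% (test); two-sided alpha 5%.

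**Assumptions, not in the protocol.** Correlation r between baseline and follow-up mBI of 0.3 to 0.6, with equal variances. For resolution, an odds ratio of 0.61 or 0.37 per SD of baseline mBI (log-odds slopes -0.5 and -1.0), with mBI as a standard normal score.

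**Plan's own figure.** The protocol gives no figure for adjustment. Its sample size of 28 is not reproduced: the usual two-proportion formula at 66.6% against 50% with 90% power gives 184 per group. At 28 per group, power is Φ[(0.166 − 1.96 × 0.1318)/0.1299] = Φ(−0.71) = 23.9%. That is a separate matter; here it only sets the starting point.

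**1. Quantitative mBI.** The ANCOVA variance relative to a follow-up-only comparison is 1 − r², times a small-sample factor of 1 + 1/(N − 4) = 1 + 1/52 = 1.019 for N = 56.

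| r | 1 − r² | × 1.019 | Saving |
|---|---|---|---|
| 0.3 | 0.91 | 0.93 | 7% |
| 0.5 | 0.75 | 0.76 | 24% |
| 0.6 | 0.64 | 0.65 | 35% |

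With 24 per group the factor is 1 + 1/44 = 1.023 and the savings are almost the same (0.91 × 1.023 = 0.93; 0.64 × 1.023 = 0.65). Before the small-sample factor, the difference detectable with 90% power at 28 per group is (1.96 + 1.28) × √(2/28) = 0.87 SD unadjusted. It falls to 0.87 × √0.91 = 0.83 SD at r = 0.3 and 0.87 × √0.75 = 0.75 SD at r = 0.5.

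**2. Values piled at zero.** Follow-up mBI may cluster at zero, so the normal-theory result was checked by simulation: share of six bleeding sites, 1 to 6 bleeding at baseline, zero-inflated follow-up, 28 per group, 6,000 runs. At r = 0.31 the variance ratio is 0.90. At r = 0.47 it is 0.75-0.79. The saving is thus about 10-25%, and ANCOVA's type I error is 4.5-5.3%.

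**3. Binary resolution.** Simulation at 28 per group with likelihood-ratio tests (20,000 runs):

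| | Unadjusted | Adjusted, OR 0.61 | Adjusted, OR 0.37 |
|---|---|---|---|
| Power, nominal 5% | 23% | 26% | 30% |
| Power at the unadjusted test's size | 23.3% | 24.4% | 27.2% |

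The second row is needed because the adjusted test rejects about 5.4-5.7% of the time under no group effect, against 4.4-4.7% unadjusted. At equal size the gain is 24.4 − 23.3 = 1.1 to 27.2 − 23.3 = 3.9 points. At 24 per group with the weaker slope, power moves only from 23% to 23.7% even before that correction. The standard error of the log odds ratio rises from 0.556 to 0.586-0.633, because the adjusted odds ratio is conditional on mBI.

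**4. Effect modification, if meant.** With baseline mBI alone in the model, equal slopes of -0.5 in both groups give a pooled odds ratio of 0.62; slopes of 0 (control) and -1.1 (test) also give 0.62. The two cases cannot be told apart. A treatment-by-mBI term separates them in principle. For a ratio of odds ratios of 0.5 per SD, however, its power is 20-25% at 28 per group and 17-22% at 24 (Wald to likelihood-ratio). The likelihood-ratio figures are slightly generous, since that test's type I error is about 6-7%. At 28 per group the median 95% CI is the estimate divided or multiplied by 3.7: for 0.5, from 0.14 to 1.85.

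**The case against.** The strongest reply is that Section 5 contains no error here. Unadjusted tests are a legitimate choice after randomisation, and the largest savings apply to quantitative mBI, whereas the sample size rests on binary resolution and the examination section dichotomises mBI for the primary outcome. That stands as to weight. It does not remove the point, because the primary objective is itself worded as a reduction in mBI, and there the saving is real and nearly free. The listed linear regression test could also carry a covariate, but none is named.

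Four stronger readings are tempting and not supported:

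- A reader might infer that the planned comparisons are biased. They are not; only precision is lost.
- A reader might infer that adjustment lifts power for resolution from 23% to 30%. Part of that rise comes from a slightly liberal test.
- A reader might credit ANCOVA with savings against a between-group comparison of change scores. Section 5 names no such comparison; its change tests are described only as change against baseline.
- A reader might infer that the logistic model leaves a stated hypothesis untested. The sentence does not exclude a treatment term, it serves the secondary objective as written, and the closing words of the fourth hypothesis may mean no more than after treatment. The gap exists only on the effect-modification reading.

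**Conclusion.** The point holds as a missed gain in precision, not as a flaw in validity. For quantitative mBI, ANCOVA would save about 7-35% of the variance of the group difference at r between 0.3 and 0.6, or about 10-25% with values piled at zero. For resolution the benefit is 1 to 4 percentage points of power at 28 per group, and close to nil at 24 if mBI is weakly prognostic. All of this rests on assumed correlations and slopes. The normal score used for resolution is also an idealisation, because eligibility requires at least one bleeding site and so truncates mBI from below. The mismatch between the fourth hypothesis, the secondary objective and Section 5 is a lesser point of wording to be settled.

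**What to change.** In Section 5:

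1. Compare quantitative patient-mean mBI between groups at 1 and 3 months by ANCOVA on group and baseline mBI. Add a rank-based check, since follow-up values may pile up at zero.
2. In the logistic model already planned, include treatment group alongside continuous baseline mBI. It then serves the secondary objective and yields an adjusted group effect on resolution as a supporting result. Keep the unadjusted risk difference with its 95% CI as the main group effect on resolution.
3. Reconcile the fourth hypothesis with the secondary objective and Section 5. Only if effect modification is meant, add a treatment-by-baseline-mBI term, labelled exploratory and reported as an estimate with CI. Otherwise reword the hypothesis to match the objective.

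The cost is a few lines of text, with no new data or visits. "The SPSS version 19.00 software" is named for all analyses; since linear and logistic regression are already listed, items 1 and 2 extend planned methods. The downsides are a conditional odds ratio with a larger standard error, a modelling assumption that needs checking, and an imprecise interaction estimate if one is added. None of this cures the separate sample-size problem.

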## ANNEX 1. Diagram

Visit Number	Day	Procedure
V-1	Screening and treatment	Informed consent Measurements of clinical variables (FMP, FMBI, FMPPD, mPI, mBI, PPDi, MRI) Microbiological test Periapical x-ray
V-2	1-Month	Measurements of clinical variables (FMP, FMBI, FMPPD, mPI, mBI, PPDi, MRI) Microbiological test
V-3	3-Month	Measurements of clinical variables (FMP, FMBI, FMPPD, mPI, mBI, PPDi, MRI) Microbiological test Periapical x-ray
